5.3 Data Cutoff Date

Associated with each analysis is a data cutoff date which will include data for all visits up to that date. The key analyses will use the data cutoff date to censor event dates, and this may result in an event date turning into a censored date. Additional sensitivity analyses without data cutoff censoring will also be done when there has been data cutoff censoring, especially when data cutoff censoring results in loss of events.

6.0 STATISTICAL ANALYSIS

Categorical variables will be summarized using counts and percentages. Percentages are based on the number of patients in the analysis set for whom there are non-missing data, unless otherwise specified.

Continuous variables, including change from baseline, will be summarized using descriptive statistics [n, mean, standard deviation (SD), minimum, median, maximum].

The rates of binary endpoints will be compared using a one-sided Pearson χ^2 test for unstratified analyses and Cochran-Mantel-Haenszel (CMH) test for stratified analyses. For the unstratified analyses, point estimates of the rates for each treatment arm and difference of the rates between treatment arms will be provided along with the corresponding 2-sided 95% confidence intervals using an exact method based on the F distribution and using a normal approximation for constructing a confidence interval for differences, respectively. For the stratified analyses, the relative risk ratio estimator will be used to contrast the treatment effects on the endpoint. Both a point estimate and a 2-sided 95% confidence interval will be calculated using a normal approximation.

Time-to-event endpoints will be summarized using the Kaplan-Meier method and displayed graphically when appropriate. Median event times and 2-sided 95% confidence interval for each median will be provided. Cox proportional hazard models will be used to explore the potential influences of the baseline stratification factor on time-to-event endpoints. The estimated hazard ratio and 2-sided 95% confidence interval will be provided.

Stratified analyses will be conducted controlling for the randomization stratification variables of disease state (IIB/IIC vs. IIIA vs. IIIB/IIIC).

Baseline is defined as the last data point prior to randomization in Part A or Part B of the study, unless otherwise stated. Baseline is defined as the last data point prior to dosing in the open-label extension of Part A, unless otherwise stated.

Patient data listings will include all enrolled or randomized patients as applicable to Part A, open-label extension of Part A, or Part B of the study. Listings will be presented by or include part of the study where appropriate, and be sorted by treatment group, site, patient number, and date (if applicable).

Statistical analyses will be carried out using SAS statistical analysis software version 9.1.3 or higher (SAS Institute, Inc., Cary, North Carolina, USA).

6.1 Patient Disposition

Patient disposition will be summarized by Part A, open-label extension of Part A, and Parts B1 and B2. The number and percent of patients who received study drug, completed each part or discontinued prematurely will be presented. The number of patients in each population, along with the number who completed the study or prematurely withdrew within each population, will be displayed. In addition, the primary reasons for early withdrawals will be summarized.

6.2 Protocol Deviations

All instances of protocol non-compliance will be tracked during the study and a list of protocol deviations will be finalized by a blinded Sponsor review prior to database lock. This final list of protocol deviations will be presented in a data listing and major deviations will be summarized using counts and percentages by Part A, open-label extension of Part A, and Part B.

6.3 Demographics and Baseline Characteristics

Demographic and baseline characteristics will be presented for Parts A, open-label extension of Part A, and Parts B1 and B2 by assigned treatment. Demographics include age, gender, race, and ethnicity. Age will be calculated using the following:

$$\text{Age} = \text{integer} [(\text{informed consent date} - \text{date of birth})/365.25].$$

Baseline characteristics include: height, weight, ECOG performance status, previous melanoma therapy, location of tumor, lymphadenectomy, pathologic staging, stage, and BRAF mutation status.

Comparability of treatment groups will be summarized in frequency tables, and descriptive statistics will be provided for quantitative variables.

6.4 Baseline History

6.4.1 General Medical History

Medical histories will be coded using Medical Dictionary for Regulatory Activities (MedDRA) Version 14.1 and summarized by body system using counts and percentages, for Parts A and B by assigned treatment. The number and percent of patients with ongoing conditions will be presented for each body system.

6.4.2 Childbearing Potential and Pregnancy Tests

Childbearing potential status and pregnancy test results will be presented for Part A, open-label extension of Part A, and Part B. All study-related procedures (other than RFS and survival follow-up) will be terminated for a female subject if she becomes pregnant.

6.4.3 Physical Examination

The number and percent of patients having an abnormal finding in the physical examination will be summarized at screening for each body system for Part A, open-label extension of Part A, and Part B. For those with abnormal findings, a listing of findings will be presented.

6.5 Concomitant and Prior Medications

All concomitant medications, including any herbal preparations, defined as non-study drug with a start date from the beginning of the Screening period through the patient's last visit in the study are to be recorded in the CRF.

Medications with partial onset dates that indicate usage from the beginning of the Screening period and medications with completely missing stop dates will be classified as concomitant.

Prior medications preceding study drug administration will be presented for Part A, open-label extension of Part A, and Part B and will be summarized for the ITT analysis set by assigned treatment. Prior and concomitant medications will be coded using the World Health Organization (WHO) Drug Dictionary Version 01Mar2012. Levels of summarization will include global, WHO Anatomic Therapeutic Chemical (ATC) Level II drug class, and WHO generic term. At each level of summarization, a patient will be counted only once for each concurrent medication he/she has within that level. The percentage of patients having had at least one medication at each level will be calculated.

Listings will be provided for all prior and concomitant medications.

6.6 Concurrent Procedures

Non protocol-specified procedures performed during the study are considered as concurrent procedures. These will be recorded on the CRF from the beginning of the Screening period through the patient's last visit in the study.

The number of patients with any concurrent procedures will be summarized for Screening Parts A and B and will be summarized for the ITT analysis set by assigned treatment. The number of patients who had a concurrent procedure performed due to an adverse event, medical history, or another reason will also be summarized.

Listings will be provided for all concurrent procedures.

6.7 Treatment Administration/Compliance

Based on the safety analysis set, administration of study drug will be presented for Part A, open-label extension of Part A, and Part B by treatment group and will be described in terms of the total number of injections administered, expected total number of injections and compliance calculated as $(\text{total number of injections administered}) / (\text{total number of injections expected}) \times 100$. Study drug exposure as well as reasons for modifications/interruptions/delays will be provided in data listings.

6.8 Part A Efficacy Endpoints

6.8.1 Analyses of Biological Endpoints

Complex immunological data will be collected from Part A patients. A description of these data and their processing is provided in the Endpoint Charter. The immunology data to be used in the statistical criterion for Part A come from two assessments: (1) IgG/IgM Western blot method, and (2) T-Cell Elispot method. Each method provides an immune response dichotomous outcome for each patient (0 = negative, 1 = positive). The DMC will be provided with unblinded results on these two dichotomous immune endpoints for each patient.

For the primary endpoint in Part A, a patient will be regarded as having a positive immune response if the IgG/IgM Western blot is positive. For the secondary endpoint in Part A, a patient will be regarded as having a positive immune response if the T-Cell Elispot method is positive.

The proportion of positive immune responses for each arm and combined seviroptimut-L will be computed and used to assess Part A immune response. The proportions will be notated as P_0 , P_1 , and P_2 , where the subscript designates the arm (0, 1, and 2 denoting placebo, 40 μ g seviroptimut-L, and 100 μ g seviroptimut-L, respectively). Data will be summarized for the proportion of patients having a positive or negative response for the IgG/IgM Western blot, the T-Cell Elispot, and either the IgG/IgM Western blot or T-Cell Elispot.

6.8.2 Immunological Statistical Success

Immunological statistical success is defined as either one of Arm 1 or Arm 2 having a higher proportion of positive immune response (defined above) being significant at the one-sided 0.10 level of significance. A relaxed significance level is justified because a high false positive probability is acceptable for this immune response evaluation. Fisher's exact test is to be used to perform these two tests. The overall likelihood of a false positive conclusion for these two comparisons will not exceed 0.20 adjusting for two tests (0.10 = 0.20/2). The following table shows approximate critical values of the difference being tested for various values of probability of success in Arm 0:

| Arm 0 Success Probability | Critical Difference |
|--|---------------------|
| 0.10 | 0.155 |
| 0.15 | 0.170 |
| 0.20 | 0.175 |
| 0.25 | 0.185 |
| Critical difference = this value or greater will be significant at the one-sided 0.10 level. | |

If only one of the two comparisons (Arm 0 versus Arm 1 or Arm 0 versus Arm 2) meets the statistical criterion then the dose associated with this arm may become the candidate dose for Part B. If both arms meet the statistical criterion, then the candidate dose may be selected based on the relative size of the proportion difference.

The dose to be used in the initiation of Part B will be based on all aspects of the analysis of the data collected and available from Part A. The primary consideration will be the statistical criterion specified above. Failure to meet statistical criteria for either Arm 1 or Arm 2 will not automatically preclude the initiation of Part B, however. The DMC is chartered to make a recommendation regarding initiation of Part B based in part on toxicity of the vaccine treatment compared to current FDA-approved treatment for resected melanoma (see DMC Charter).

The seviprotimut-L dose selected for the initiation of Part B is 40 μ g.

The analysis of other immunological data will be open-ended with the goal of identifying any immunological changes associated with the initiation of vaccine therapy.

6.9 Parts B1 and B2 Efficacy Endpoints

6.9.1 Overall Survival (OS)

The survival analysis objective is to ascertain whether the survival time distribution for patients randomized to the experimental arm is consistent with longer survival as compared to patients randomized to the control arm. All randomized patients will be included in the primary survival analysis in Part B2 or the descriptive secondary analysis of survival in Part B1 according to the randomized arm (intent-to-treat).

The following dataset variables (actual variable names may be different in the analysis datasets) are to be derived from the study database associated with a data cutoff date and used to perform the analysis of survival associated with that data cutoff:

| Variable Name | Label | Definition |
|---------------|----------------------------|---|
| strat | Randomization Stratum | A variable having a unique value for each possible combination of factors used in the stratified randomization scheme. |
| randd | Date of Randomization | Date patient is randomized. |
| expi | Experimental Arm Indicator | expi = 1 if patient is randomized to the experimental arm. expi = 0 if patient is randomized to the control arm. |
| di | Death Indicator | 
• di = 1: The patient is known to be dead. The value of dd (see below) is the date of death.• di = 0: The patient is not known to be dead and is not known to have had a competing event. The value of dd is the date the patient is last known to be alive for a patient that has yet to experience either death or a competing event (see below). di = 0 indicates that dd is a censored date. |

| | | |
|-----------|---------------|--|
| | | 
• di = -1: The value of dd is the date the patient was classified as having a competing event. di = -1 indicates that dd is the date of a competing event. |
| dd | Date of Death | The date of death (di = 1) or the date last known to be alive (di = 0) or the date of competing event (di = -1). See data imputation rules previously specified. |
| dt | Time to Death | dt = dd - randd |

Imputation of missing dates will follow the rules previously specified. Competing events for death are “definite” lost to follow-up and withdrawal of consent for continued vital status assessments. While both of these competing events are subject to revision for an individual patient with the passage of time it is considered unlikely. The primary analysis will consist of executing two SAS procedures, a stratified logrank test for the test of the hypothesis and a proportional hazard regression to estimate the hazard ratio and its 95% confidence interval. Model SAS code for these two procedures is as follows:

```
proc lifetest;
  strata strat / group=expi test=logrank;
  time dt*di(0,-1);
run;

proc phreg;
  class strat;
  strata strat;
  model dt*di(0,-1)=expi / rl ties=exact;
run;
```

The significance of the logrank test will be assessed in Part B2 by referring the one-sided stratified logrank test P value to the significance criterion applicable to the analysis. The one-sided stratified logrank test P value, P_1 , is to be computed as follows from the hazard ratio estimate from the proportional hazard regression, HR, and the two-sided P value from stratified logrank test, P_2 : If $HR < 1$ then $P_1 = P_2/2$. If $HR \geq 1$ then $P_1 = 1 - P_2/2$. The analysis of survival for Part B1 will be descriptive and use the same methods, with a focus on confidence intervals of estimates.

Notes:

- These analyses must be stratified (3).

- When there are competing events then censoring competing events provides a between-arm test of the event of interest (4).

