5.2.10 Survival Monitoring of Subjects after Recurrence

Subjects with confirmed recurrent disease (see Section 9.3) (and who are not continuing to receive study drug per section 7.2.4) will no longer attend study visits, but will be monitored for survival at least every 6 months (+/- 14 days) through telephone contact until the study is terminated/completed or the subject is withdrawn or lost to follow-up. At the telephone contact, the subject will be asked for information on any additional cancer therapy he/she has started. Contact in-person is acceptable in lieu of a telephone contact. Survival of subjects lost to follow-up by telephone will be tracked by the investigator through the Social Security Death Index in the US, or other similar database outside the US if available.

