9.3 Part B Clinical Efficacy Parameters

Survival time is computed based on the date of death if the subject is known dead or the date last known to be alive (censored). Zero time for a subject is the date of randomization.

Recurrence-free survival time (RFS) is computed from the earliest of the date of recurrence or death or, if without recurrence or death, the date last assessed for recurrence without a diagnosis of recurrence (censored). The date of recurrence is specified as the first date a recurrence is suspected, which is later confirmed by biopsy. In the rare cases where biopsies are not clinically appropriate (e.g., brain metastases), the recurrence date will be set by the treating clinician's medical judgment. Zero time for a subject is the date of randomization.

Recurrence will be monitored through tumor imaging (as specified in Section 9.3.1) every 6 months until recurrence, death, subject withdrawal, early termination or completion of the study.

LDH is also monitored every 3 months for early indication of possible recurrence. LDH elevations of 1.5 X ULN (or greater) will be followed up with radiological scans, provided there are no other obvious medical reasons for the elevated LDH.

Recurrence is defined as the occurrence of the following events:

- Loco-regional relapse
- Distant metastasis
- A new melanoma that is likely unrelated to the original primary lesion

Investigators are required to obtain biopsies of recurrent tumors to provide pathologic evidence of recurrence unless the recurrence is in the brain. In the case of multiple lesions during an imaging examination, biopsy of at least one lesion should be obtained.

As the determination of recurrence will primarily rely on biopsies, there will be no central reading of CT scans to confirm recurrence.

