Key analyses may depend on the date of the first occurrence of an event associated with the endpoint. When the event has yet to occur the analysis will nonetheless require an analytical date be available for the analysis. These are known as censored or truncated dates. A censored date is the date of the most recent assessment for the event for a patient for which the event of interest has yet to occur and for which additional time may lead to observation of the event of interest. A truncated date is the date of a

competing event that precludes the observation of the event of interest. The distinction between designating an analytical date as censored or truncated will depend on the purpose of the analysis and will be designated for each analysis. For example, if death is the event of interest and a patient is still alive and being followed for the date of death then the date last known alive is a censored date, whereas the date a patient withdraws consent for continued follow-up of vital status (a competing event) is a truncated date. Please note that the nature of the competing event will dictate whether the competing event is permanent. For example, the date of death for a patient who has withdrawn consent may later become known passively from governmental death records.

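### For overall survival, SAP 6.9.1 censors patients definitely lost to follow-up at the date they were classified as lost, whereas Protocol 9.3 allows only date of death or date last known alive

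*SAP*

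**What the plan says.** OS is a primary endpoint of Part B2 and descriptive in Part B1. Protocol 9.3 defines it with two possible dates: "Survival time is computed based on the date of death if the subject is known dead or the date last known to be alive", the latter being censored.

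SAP 6.9.1 has three states. Deaths are `di = 1`. For patients not known to be dead there are two date rules:

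- `di = 0`: "The value of dd is the date the patient is last known to be alive for a patient that has yet to experience" one of the other two outcomes.
- `di = -1`: "The value of dd is the date the patient was classified as having a competing event".

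The text after the table says which events are meant: "Competing events for death are “definite” lost to follow-up and withdrawal of consent for continued vital status assessments". The model code uses `dt*di(0,-1)`, so both states are censored at `dd`.

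SAP 4.6 gives the general idea of a truncated date, and its example is withdrawal: "the date a patient withdraws consent for continued follow-up of vital status (a competing event) is a truncated date". It has no example for loss to follow-up.

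Protocol 5.2.10 asks for survival contact at least every 6 months after recurrence and adds a back-up: "Survival of subjects lost to follow-up by telephone will be tracked by the investigator through the Social Security Death Index", or a similar database outside the US if there is one.

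For Section 6.9.1, Addendum #1 changes only the source of the randomization date, the source of the stratum and some SAS options. For recurrence-free survival (Section 6.9.2) it does redefine the date, setting it to last known alive for a patient without recurrence or death.

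**The concern.** On the date a patient withdraws vital-status consent, the patient is known to be alive. On the date a patient is classified as lost, status is by definition unknown, and the last evidence of life is older. Dating the censoring at classification keeps the patient in the risk set through a period in which a death may not be seen. Time at risk rises with no matching chance of an event, so the estimated death hazard falls and the Kaplan-Meier curve sits slightly too high.

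If this happens equally in both arms it largely cancels in the comparison. If one arm loses more patients, or is classified more slowly, that arm looks better. OS is projected to need 13 years from the start of accrual, which leaves room for loss to accumulate. None of the OS sensitivity analyses listed in SAP 6.9.3.1 varies this date. The SAP definition of a Part B2 primary endpoint also departs from the protocol's definition.

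**Working it through.** **Design figures.** Inputs from SAP 5.2.2: 432 deaths at the final analysis, 157 projected at the interim, one-sided level 0.002625 at each, 1:1 allocation. With z = 2.791, the critical HR is exp(−2z/√deaths).

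- Final: exp(−2 × 2.791/√432) = exp(−0.2686) = 0.764. The SAP states 0.764.
- Interim: exp(−2 × 2.791/√157) = exp(−0.4455) = 0.640. The SAP states 0.637.

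These depend only on the number of deaths and the significance level. The censoring date enters neither, so no design figure moves under either rule.

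**Why only imbalance matters for the HR.** Suppose an arm loses a fraction r of patients per year and classification follows last contact by L years. The classified-date rule lengthens time at risk by a proportion of about rL and adds no deaths, so the arm's hazard is multiplied by about exp(−rL). The ratio of the HR under the SAP rule to the HR under the protocol rule is therefore about exp(−(r_V − r_P) × L), which is 1 when loss and lag are equal.

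For r_P = 0.01 and r_V = 0.03:

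- L = 0.5: exp(−0.01) = 0.990
- L = 1: exp(−0.02) = 0.980
- L = 2: exp(−0.04) = 0.961
- L = 3: exp(−0.06) = 0.942

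**Simulation.** Trials were simulated and analysed by stratified logrank and Cox, with 400 replicates per scenario. Each data set was analysed under both date rules, with analysis at 432 deaths. Stage-specific death hazards were fitted to 157 deaths at 3.93 years and 432 at 13.0 years. These hazards, a 1-year accrual ramp, the loss rates and the lags are assumptions.

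HR under the classified-date rule divided by HR under last known alive:

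| Annual loss, placebo / vaccine | True HR | 0.5 y lag | 1 y | 2 y | 3 y |
|---|---|---|---|---|---|
| 1% / 1% | 0.6667 | 0.9999 | 1.0001 | 1.0007 | 1.0020 |
| 3% / 3% | 0.6667 | 1.0001 | 1.0008 | 1.0032 | 1.0075 |
| 1% / 3% | 0.6667 | 0.9903 | 0.9813 | 0.9650 | 0.9511 |
| 1% / 3% | 1 | 0.9900 | 0.9805 | 0.9626 | 0.9466 |

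The simple formula and the simulation agree closely. In the equal-loss scenarios shown, the unobserved time adds between 0.5% (1% loss, 6-month lag) and 8.5% (3% loss, 3-year lag) to total person-time. That is the source of the Kaplan-Meier inflation. With 400 replicates the simulation cannot measure the error rate at 0.002625, so no claim is made about it.

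**Deaths in the gap.** Assume 5% to 15% of 800 patients are lost, with a lag of 0.5 to 2 years. The gap is then 800 × 0.05 × 0.5 = 20 to 800 × 0.15 × 2 = 240 patient-years. The average death rate is −ln(1 − 432/800)/11.5 = 0.0675 per year, where 11.5 is 13 years less half of the 3-year accrual. Expected deaths are 800 × p × (1 − exp(−0.0675 × lag)), from 1.3 (p = 0.05, 0.5 y) to 15.2 (p = 0.15, 2 y). Deaths in the gap that go unseen are missed under both rules.

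**The case against.** The strongest reply is that the wording is not settled. The `dd` row of the same table, and SAP 4.6, speak of the date of the competing event, which for loss to follow-up could be taken as the date contact ceased. Cutoff rule 9 in Addendum #1 refers to endpoints censored at date last known alive, which suggests the sponsor may work that way. This lowers confidence. It does not remove the conflict: the `di` row says how the date is set, and nothing in the Addendum replaces it.

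The affected group is also narrow. A patient merely out of contact stays at `di = 0`, dated at last known alive. Protocol 6.2.3 withdraws patients from vital-status follow-up only at their own request. Status can later be revised, although SAP 6.9.1 considers that unlikely. Blinding of patients and sites makes unequal loss less likely. Part B2 is itself conditional on Part B1. All of this stands, and it limits the size.

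Two stronger readings are tempting and not supported. A reader might infer that the rule credits survival time that nobody observed. Where a death-index search is done, the gap is at least partly observed; nor do the documents say that a search precedes classification, or how long classification takes. A reader might also infer that the rule leaves 1 to 15 deaths uncounted. Censoring at last known alive would not count them either; the rule changes only time at risk.

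Finally, the protocol's rule has its own weakness. Deaths found passively after loss still count at the death date, while other lost patients are cut back to last contact, which pulls estimated survival down a little. That is a reason to report such deaths openly. It does not justify departing from the protocol's definition, and a documented confirmation of life can move the last-known-alive date forward.

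**Conclusion.** The point holds as a conflict between SAP and protocol on a Part B2 primary endpoint, with a clear mechanism and a small expected effect. Read as written, SAP 6.9.1 keeps definitely lost patients at risk until classification, contrary to Protocol 9.3, and Addendum #1 leaves this in place.

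Survival curves are modestly inflated in both arms. Across the equal-loss scenarios the HR moves by less than 1%. A shift of about 1% to 4% in favour of the arm with more loss needs an imbalance such as 1% against 3% per year together with a lag of 0.5 to 2 years. Those rates and lags are assumptions. Contact at least every 6 months after recurrence makes a lag of that order plausible there, but it is not a stated figure or a firm lower limit. Severity is minor and confidence moderate, because the table's wording leaves some room and *definite* is not defined.

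**What to change.** In the SAP 6.9.1 table, for `di = -1` due to loss to follow-up, set `dd` to the date last known alive, including any later date on which a documented contact or record confirms the patient alive. Keep the withdrawal date for withdrawn vital-status consent. Run the classification-date version only as a sensitivity analysis, and state there what makes a loss definite. Report by arm the deaths found from registries after loss of contact, so that the downside described above can be judged.

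The cost is a sentence or two in the SAP, one derivation line and one extra run. The SAS code is unchanged because 0 and −1 are both already censored. No new data are needed, since date last known alive is already required for `di = 0`. The change does not recover uncounted deaths and leaves 432 deaths, the significance levels and the critical HRs as they are.
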